3 OBJECTIVES AND ENDPOINTS

OBJECTIVES	ENDPOINTS
Primary	
To evaluate the efficacy of IXT-m200 in preventing or reducing relapse to stimulant use	Percent of 20 weeks abstinent from stimulants following a 4-week grace period (between Week 5 and Week 25) as measured by saliva screens and by self-report via smartphone app.
Secondary	
To evaluate the efficacy of IXT-m200 in increasing the number of participants achieving early remission	Proportion of responders at Week 25 as measured by DSM-5 criteria. A responder is a participant who meets the definition of early remission, i.e., ≥ 3 months and < 12 months without meeting DSM-5 criteria, while disregarding the result for craving.
To evaluate the efficacy of IXT-m200 in improving the proportion of participants achieving stimulant abstinence	Complete abstinence during the last month of study drug treatment (between Week 21 and Week 25), as measured by saliva screens and by self-report via smartphone app.
To evaluate the efficacy of IXT-m200 in improving participant-rated quality of life	Change from screening in participant-rated quality of life as measured by the Treatment Effectiveness Assessment (TEA) at Week 13, 25, and Week 33.
To evaluate the safety of multiple intravenous doses of IXT-m200	Safety and tolerability of IXT-m200 assessed by physical examinations and vital sign, AE, ECG, and clinical laboratory testing.
To evaluate the immunogenicity of multiple doses of IXT-m200	Number of participants with anti-IXT-m200 antibody levels that are confirmed positive and have titers more than three times the minimum required dilution.
Exploratory	
To evaluate the efficacy of IXT-m200 in improving the length of sustained abstinence	Number of sequential weeks of abstinence from the end of treatment visit (Week 25), defined as four weeks after the final planned treatment visit (Week 21) as measured by saliva screens and by self-report via smartphone app.
To evaluate the efficacy of IXT-m200 in improving post-treatment abstinence	Point prevalence abstinence (last 7 days) as measured by saliva screens and by self-report via smartphone app at Week 25, Week 29, and Week 33.
To evaluate the efficacy of IXT-m200 in preventing or reducing relapse to stimulant use	Weekly abstinence from stimulants following a 4-week grace period (between Week 5 and Week 25) as measured by saliva screens.

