To evaluate the efficacy of IXT-m200 in reducing the adverse outcomes associated with MUD	Difference between number of adverse outcomes recorded between Week 5 and Week 33. Adverse outcomes include those queried in the Adverse Outcomes Assessment and also suicide and overall mortality.
To evaluate the efficacy of IXT-m200 in increasing the number of participants achieving early remission	Proportion of responders at Week 33 as measured by DSM-5 criteria. A responder is a participant who meets the definition of early remission, i.e., ≥ 3 months and < 12 months without meeting DSM-5 criteria while disregarding the result for craving.
To evaluate the efficacy of IXT-m200 in improving clinician-rated response to treatment	Difference between groups in Clinical Global Impression of Change (CGIC) at Week 13, 25, and Week 33.
To evaluate the efficacy of IXT-m200 in improving patient-rated response to treatment	Difference between groups in Patient Global Impression of Change (PGIC) at Week 13, 25, and Week 33.

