9.4.3.2 COMPLETE ABSTINENCE DURING LAST MONTH OF TREATMENT

The second secondary efficacy endpoint is the complete abstinence during the last month of study drug treatment (between Week 21 and Week 25), as measured by saliva screens and by self-report via smartphone app. A modified SRPHK1 algorithm⁸ will be used to derive if a day is a “use day” or an “abstinent day” (see Section 9.4.2). A participant will be categorized as fully abstinent if the imputation algorithm resolves to zero days of use; otherwise, a participant will be categorized as not abstinent (failure).

The proportion of participants achieving complete abstinence will be compared in each IXT-m200 dose group versus the placebo group using both an odds ratio and a risk difference. The analysis approach is identical to that for the first secondary endpoint as both are binary outcomes.

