Objective: To evaluate the efficacy of IXT-m200 in improving patient-rated response to treatment.	Endpoints: Difference between groups in Patient Global Impression of Change (PGIC) at Week 13, 25, and Week 33. Clinical Question: Does adding IXT-m200 to standardized CBT program improve PGIC at Week 13, 25, and Week 33, relative to the CBT program alone in treatment-seeking participants regardless of IXT-m200 interruption or discontinuation, for any reason? Estimand: The difference in CGIC at Week 13, 25, and Week 33, between the IXT-m200 and placebo groups in treatment-seeking individuals with MUD. All observations will be used, regardless of whether a participant discontinued treatment early. Missing values will not be imputed.

Table 3 Exploratory Efficacy Objectives and Endpoints

Exploratory Objectives	Endpoints
To evaluate the efficacy of IXT-m200 in increasing the number of participants achieving early remission.	Responders at Week 33 as measured by DSM-5 criteria. A responder is a participant who meets the definition of early remission, i.e., ≥3 months and <12 months without meeting DSM-5 criteria while disregarding the result for craving.
To evaluate the efficacy of IXT-m200 in reducing the number of adverse outcomes from the Adverse Outcomes Assessment.	The difference between groups in the number of adverse outcomes reported at Week 13, 25, and Week 33.
To evaluate the efficacy of IXT-m200 in preventing or reducing relapse to stimulant use, as measured by self-report surveys.	Percent of days abstinent from stimulants following a 4-week grace period (between Week 5 and Week 25) as measured by self-report.
To evaluate the efficacy of IXT-m200 in improving the length of sustained abstinence.	Number of sequential weeks of abstinence from the end of treatment visit (Week 25), defined as four weeks after the final planned dose of study drug (at Week 21), as measured by saliva screens.
To evaluate the efficacy of IXT-m200 in improving post-treatment abstinence.	Point prevalence abstinence (last 7 days) as measured by saliva screens at Week 25, Week 29, and Week 33.
To evaluate the efficacy of	Complete abstinence during the last month of study drug treatment (between Week 21 and Week 25), as measured by saliva screens.

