4.7.1.1. Definition of endpoints

The corresponding secondary endpoints are:

- 1. Change from screening in participant-rated quality of life as measured by the Treatment Effectiveness Assessment (TEA) at Week 13, 25, and Week 33.
- 2. Responders at Week 25 as measured by the DSM-5 criteria. A responder is a participant who meets the definition of early remission, i.e., ≥3 months and <12 months without meeting DSM-5 criteria, while disregarding the result for craving.
- 3. Difference between groups in Clinical Global Impression of Change (CGIC) at Week 13, 25, and Week 33.
- 4. Difference between groups in Patient Global Impression of Change (PGIC) at Week 13, 25, and Week 33.

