A secondary objective is to evaluate the efficacy of IXT-m200 in improving the proportion of participants achieving stimulant abstinence, defined as complete abstinence during the last scheduled month of study drug treatment (between Week 21 and Week 25), as measured by saliva screens.

A participant will be categorized as fully abstinent if they have zero days of use (between Week 21 and Week 25); otherwise, a participant will be categorized as not abstinent (failure). Participants who withdraw or discontinue prior to Week 5, or do not have any reported saliva or self-report use data between Weeks 5 and 25 will not be included in the analysis.

The proportion of participants achieving a response will be compared in each IXT-m200 group versus the placebo group using a stratified Mantel-Haenszel statistic with stratification level of past-month METH use at screening (discrete). The output will provide the risk difference between each IXT-m200 dose group and the placebo group, two-sided p-values, and 95% confidence intervals using the Miettinen-Nurminen (score) confidence limits.

Reduction in the frequency of METH use over time

An additional exploratory objective is to evaluate the efficacy of IXT-m200 in reducing the frequency of METH use over time. For each day from the start of Week 5 through the end of Week 25, abstinence or use will be based on the self-reported use in the previous seven days. The number of use days in each week will then be determined.

The weekly total for a subject will be derived by counting the number of use days among the non-missing days and normalizing to a seven-day period. For example, for a subject with 1 use day among 4 non-missing days and 3 missing days in a given week, the number of use days (X) will be derived as X = (1/4)*7 = 1.75. No rounding will be performed. If a subject has all missing days in a given week, that week will not be imputed and therefore will not contribute to the analysis.

The number of use days per week will be summarized in a table presenting the mean and standard deviation for each treatment group, at each of the weeks from 5 to 25. No formal statistical testing will be performed for this endpoint. A plot of these group means across weeks will be provided.

[figure not shown]
A spaghetti plot will also be provided to show the use days per week by subject throughout the study. Pseudo-R code for the plot is included in Exhibit 7, and an example of the plot is included in Exhibit 8.

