# Spaghetti plot
plot <-ggplot(data=weeksdat, aes(x=WEEK, y=usedays j, group=SUBJID))
plot +
 geom line(aes(col = TRT GRP)) +
 #geom point() +#
 xlim(0,25) +
 v_{1}(-.25,7.25) +
 labs(title = "Spaghetti Plot of Participant Weekly Meth Use Days\n",
    x="Study Week", y="Number of Meth Use Days", color="Treatment Group\n") +
 scale x continuous(breaks=seq(0,26,2)) +
 scale y continuous(breaks=seq(0,7,1))
 theme bw()
```

Exhibit 8 Weekly Meth Use Days Spaghetti Plot

Spaghetti Plot of Participant Weekly Meth Use Days

Proportion of participants with *n* or fewer use days between Week 5 and Week 25 Measured by Self-Report

The proportion of participants with n or fewer use days between Week 5 and Week 25, where n ranges from 0 to 20 will be summarized. A secondary endpoint is Complete Abstinence during the last 4 weeks. This analysis will expand that to the last 20 weeks and explore a range of use days from 0 (complete abstinence) to 20 (an average of one use day a week).

A "use day" or "abstinent day" will be based on self-report surveys. Missing survey responses will be imputed assuming use for that day. The summary will be descriptive only, presenting the number and percentage of "responders," defined as subjects with n or fewer use days between Week 5 and Week 25 (Study days 29 to 169). A continuous responder curve will be produced with the number of use days on the horizontal axis and percent of subjects on the vertical axis, with a line for each treatment group. Since the criteria for a responder becomes less strict as n increases, both curves would be expected to be near 0% at n=0, and increase as they move to the right. The graph will allow a visual examination of potential separation between treatment groups. Pseudo-R code for the plot is included in Exhibit 9. For number of use-days from 0 to 140 (20 weeks), calculate the proportion of subjects with n use-days or less. Exhibit 10 shows an example of the plot.

Exhibit 9 Pseudo-R Code for Continuous Responder Curve Plot

[figure not shown]
plot(NA,NA,xlim=c(0,175),ylim=c(0,1),xaxt='n',yaxt='n',xlab='Number of Use Days', ylab='Proportion of Responders',main='Continuous Response Curve') for(i in 1:18){

```
abline(v=(i-1)*10,col=rgb(0,0,0,0.05))
}
for(i in 1:11){
   abline(h=(i-1)/10,col=rgb(0,0,0,0.05))
}
lines(seq(0,max(trt$DAY)),prop_resp_t,col=rgb(0.2,0.7,0.9,1))
lines(seq(0,max(placebo$DAY)),prop_resp_c,col=rgb(1,0.5,0,1))
   axis(1,seq(0,180,10))
   axis(2,seq(0,1,0.1))

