4.13. Changes to Protocol-Planned Analyses

• There are no changes to the analyses planned in the protocol.

5. Supporting Documentation

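### The SAP's secondary efficacy list differs from protocol v5 on complete abstinence, CGIC and PGIC, contradicts itself on complete abstinence, and is accompanied by a statement that nothing changed

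*SAP*

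**What the plan says.** **Protocol v5.** Section 3 has three secondary efficacy endpoints: early remission at Week 25 by DSM-5 criteria, change in TEA at Weeks 13, 25 and 33, and "Complete abstinence during the last month of study drug treatment (between Week 21 and Week 25), as measured by saliva screens and by self-report" through the app. Sections 9.1 and 9.4.3 repeat this list. The objective "To evaluate the efficacy of IXT-m200 in improving clinician-rated response to treatment", measured by CGIC, stands in the exploratory part of section 3, as does its patient-rated counterpart, PGIC. Table 2 of section 9.4.9 again plans both as exploratory.

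**SAP.** The introduction says the plan is based on protocol version 5 of 3 February 2023. Table 2 and section 4.7 give four secondary efficacy endpoints: TEA, early remission, CGIC and PGIC. For example, 4.7.1.1 lists "Difference between groups in Clinical Global Impression of Change (CGIC) at Week 13, 25, and Week 33". Table 3 places the following among the exploratory endpoints: "Complete abstinence during the last month of study drug treatment (between Week 21 and Week 25), as measured by saliva screens".

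The running text of SAP 4.8, Exploratory Analyses, uses different labels. The complete abstinence analysis opens with "A secondary objective is to evaluate the efficacy of IXT-m200 in improving the proportion of participants achieving stimulant abstinence". Both responder-curve analyses, by self-report and by saliva, state: "A secondary endpoint is Complete Abstinence during the last 4 weeks". The analysis of self-reported percent days abstinent is also introduced as a secondary objective, although Table 3 lists it as exploratory and the protocol does not list it.

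On departures from the protocol, SAP 4.13 says only: "There are no changes to the analyses planned in the protocol".

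**The concern.** The secondary list tells the reader of the final report which efficacy results, after the primary, were singled out in advance. Here the protocol and the SAP give different lists, and the SAP's own text disagrees with its tables. The section meant to disclose departures denies that there are any. A report written from this SAP could present CGIC and PGIC as planned secondary evidence and complete abstinence as a side analysis, and a reader relying on 4.13 would not know that the protocol says the opposite.

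The SAP's precedence rule adds to the problem. Both documents let the SAP override the protocol's statistical text, so an undisclosed difference takes effect without anyone having to justify it.

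**Working it through.** This is a comparison of lists. The only power figures in the documents are for the primary endpoint. They reproduce (40 against 40 at 0.73 SD gives 89.7% by the noncentral t, against 90% stated) and do not bear on this point.

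**Step 1: status of each endpoint.**

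| Endpoint | Protocol v5 (3, 9.4.3, Table 2) | SAP Tables 2 and 3, 4.7 | SAP 4.8 running text |
|---|---|---|---|
| Early remission, Week 25 | secondary | secondary | no conflict |
| TEA, Weeks 13, 25, 33 | secondary | secondary | no conflict |
| Complete abstinence, Weeks 21 to 25 | secondary | exploratory | secondary (three places) |
| CGIC, Weeks 13, 25, 33 | exploratory | secondary | no conflict |
| PGIC, Weeks 13, 25, 33 | exploratory | secondary | no conflict |
| Percent days abstinent, self-report | not listed | exploratory | secondary |

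**Step 2: other differences for complete abstinence** (protocol 9.4.3 to 9.4.3.2 against SAP 4.8).

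- Data source: saliva and self-report combined by the modified SRPHK1 algorithm, against saliva alone.
- Analysis: a binomial identity-link model adjusted for stratum, with an odds ratio as well, against a stratified Mantel-Haenszel risk difference with Miettinen-Nurminen limits.
- Participants: the ITT population, against ITT minus those who left before Week 5 or have no use data in Weeks 5 to 25.

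The methods for CGIC and PGIC also moved, from ANCOVA to Kruskal-Wallis. Each of these differences contradicts SAP 4.13.

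**Step 3: what the SAP version table discloses.** It logs changes to endpoints (1 December 2021), internal and FDA suggestions on objectives and endpoints (21 March 2023), a corrected exploratory endpoint (1 June 2023) and a new order of endpoints (14 July 2023). None of these entries says that an endpoint moved between secondary and exploratory. The July 2023 entry gives protocol changes as its reason, yet the protocol cited is still v5 of February 2023, with the list shown above.

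**Step 4: does the relabelling change the number of tests?** Count one test per endpoint and visit, per dose group.

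- Protocol secondary list: TEA 3 + early remission 1 + complete abstinence 1 = 5.
- SAP secondary list: TEA 3 + early remission 1 + CGIC 3 + PGIC 3 = 10. Four tests (TEA 3, early remission 1) are on both lists.
- All five endpoints, whatever their label: 3 + 1 + 1 + 3 + 3 = 11 in both documents.

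If the tests were independent and every null hypothesis true, the chance of at least one p<0.05 would be 1 − 0.95^5 = 22.6% within a list of 5 and 1 − 0.95^10 = 40.1% within a list of 10. Across all 11 it is 1 − 0.95^11 = 43.1% under either document. The labels move tests between boxes and add none.

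**The case against.** **The SAP is allowed to differ.** Protocol 9.4.1 and the SAP introduction both say so, and the version table signals endpoint changes several times, once citing FDA input. This stands, so the new list is not improper in itself. It does not rescue 4.13, which denies any change, and no version entry names the reclassification.

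**The SAP's intended list is clear.** Table 2, section 4.7 and 4.7.1.1 agree on the same four endpoints, and the conflicting sentences all sit under the exploratory heading. This carries some weight: an analyst would probably follow Table 2. A report author would still find complete abstinence described as secondary three times in the governing document.

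**No error-rate control is lost.** Correct. Protocol 9.4.3 and SAP 2.3 make no multiplicity adjustment, p-values are nominal, and there is no hierarchy or gate. A reader might take the rise from 22.6% to 40.1% as inflation of false positives. The documents do not support that, because these endpoints are compared between groups in both documents and the total stays at 11.

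**Outcome-driven selection.** A reader might infer it from the current SAP's date, 1 May 2024, and its statement that the study stopped before Cohort 2. The documents do not support that either. They date neither the interim review nor the reclassification, and the May 2024 version entry lists only PK endpoints and an imputation correction. Text carried over from an older plan is also plausible. Protocol amendment 3 (July 2022) took CGIC and PGIC out of the protocol's hypotheses and secondary analysis text, and SAP Appendix 1 still shows a screening window from Day -60 and tapering recovery coaching, neither of which matches protocol v5. Carry-over is likewise only an inference.

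**Conclusion.** The concern holds as a fault of consistency and disclosure. One protocol secondary efficacy endpoint has become exploratory, two exploratory endpoints have become secondary, one SAP endpoint absent from the protocol carries two labels, and the statement in 4.13 is wrong. Two of the three protocol secondary efficacy endpoints, TEA and early remission, keep their status, so the list is partly changed, not replaced.

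The consequence is for pre-specification and for how the report presents its secondary evidence. It is not a matter of type I error, and the percentages under the check should not be quoted as its cost. Nothing in the documents establishes the timing of the change or the motive for it. The conclusion rests only on reading protocol v5 and the current SAP side by side, with v5 as the version the SAP itself names.

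**What to change.** - Give complete abstinence, CGIC, PGIC and self-reported percent days abstinent one status each, used throughout SAP Tables 2 and 3, 4.7 and 4.8.
- Use the protocol v5 status unless a documented reason that predates unblinded review supports the new list. Without such a reason, report complete abstinence as a protocol-specified secondary endpoint, with the protocol's definition (saliva and self-report) and analysis.
- Correct the four sentences in 4.8 to match: the openings of the percent-days and complete abstinence analyses, and the remark in each responder-curve analysis.
- Replace 4.13 with a dated list of every departure from protocol v5, covering status, data source, analysis method and exclusions. Mark each as made before or after the unblinded interim review.

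The cost is SAP wording, table shells and a small amount of extra analysis if complete abstinence is run to the protocol's definition. The downside is that CGIC and PGIC may lose secondary status.

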1.2. Study Design

InterveXion's protocol M200C-2201 is a Phase 2, double-blind, placebo-controlled, multiple-dose study of the safety and efficacy of monthly intravenous (IV) doses of IXT-m200 in treatment-seeking individuals with METH use disorder. The study was stopped before enrolling Cohort 2. As such, any reference to Cohort 2 in this document no longer applies, but has been retained for reference.

The study consists of two cohorts:

- In Cohort 1, approximately 60 participants will be randomized in a 2:1 ratio to IXT-m200 1.5 g or placebo (saline).
- In Cohort 2, approximately 60 participants will be randomized in a 2:1 ratio to the recommended dose of IXT-m200 or placebo based on the interim analysis at the end of Cohort 1. If the interim analysis recommends maintaining a dose of 1.5 g, then the sample size will be recalculated.

In each cohort, participants will receive either study drug (IXT-m200 at the cohort-specific dose or placebo) at the beginning of Weeks 1, 5, 9, 13, 17, and 21. All participants will also participate in seven sessions of a standardized cognitive behavioral therapy (CBT) program which will be delivered by a trained therapist; the first dose of IXT-m200 or placebo is intended to be given on the same day of initiation of CBT. For Cohort 1, the participants will participate in the CBT sessions during their monthly visits. For Cohort 2, participants will go to the clinic weekly for saliva drug tests and will participate in CBT sessions every two weeks, starting with Week 1. Participants will be followed at monthly intervals through Week 33. Cohort 1 will use app-based assessments to monitor between visits and Cohort 2 will use TLFB to monitor between visits. Schema 1.2 in the protocol displays the schematic of the study design for Cohort 1, and Appendix 1 shows the schedule of events. The first four weeks of treatment will be considered a grace period, designed to accommodate the likelihood that participants will relapse initially and experience the effects of IXT-m200. It further allows participants time to absorb and incorporate some of the skills taught by cognitive behavior therapy. METH use endpoints will be analyzed in the weeks following the grace period.

The cohorts will enroll sequentially, beginning with Cohort 1. Once the last participant in Cohort 1 has available Week 25 data (or has previously discontinued), the Data and Safety Monitoring Board (DSMB) will review an interim analysis report that includes efficacy and safety data. Based on that interim analysis, the DSMB may recommend whether to proceed to Cohort 2 and which dose to use for the IXT-m200 group (e.g., escalate to 3.0 g, continue at 1.5 g, or reduce). If the DSMB recommends continuing dosing at 1.5 g in Cohort 2, the sample size will be recalculated based on the pooled standard deviation of the observed primary endpoint estimate in Cohort 1. The DSMB may also recommend that the study be stopped early if there is sufficient evidence that any of the circumstances in protocol section 10.1.2 apply.

The Sponsor will make the ultimate decision as to whether to accept the DSMB's recommendation. The Sponsor may have access to group-level data but will not have access to unblinded participant-level data at the time of the interim analysis. The Sponsor will have ongoing access to blinded individual participant data from saliva tests and daily self-reported drug use surveys.

Participants will continue the study in Cohort 1 through Week 33 while the interim analysis is ongoing.

2. Statistical Hypotheses and Testing

